10.4.2. Breastfeeding

It is unknown whether plamotamab is secreted in human milk. Since it is known that antibodies can be secreted in human milk, a risk to the newborns/infants cannot be excluded. A decision should be made whether to discontinue breastfeeding or to discontinue plamotamab, taking into account the benefit of breastfeeding for the child and the benefit of plamotamab therapy for the woman.

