2.3.2. Tafasitamab Product Description

Tafasitamab (tafasitamab-cxix) is a CD19-directed cytolytic antibody indicated for use in the US in combination with lenalidomide for the treatment of adult patients with R/R DLBCL not otherwise specified (NOS), including DLBCL arising from low-grade lymphoma, and who are not eligible for ASCT. Tafasitamab is also approved in the EU and is indicated in combination with lenalidomide followed by tafasitamab monotherapy for the treatment of adult patients with relapsed or refractory DLBCL who are not eligible for ASCT. Tafasitamab is a humanized CD19-directed cytolytic monoclonal antibody that contains an IgG1/2 hybrid Fc-domain with 2 amino acid substitutions to modify the Fc-mediated functions of the antibody. It is produced by recombinant DNA technology in mammalian cells (Chinese hamster ovary). Tafasitamab has a molecular weight of approximately 150 kDa (see US [Monjuvi[®] PI, 2021](#); EU [Minjuvi[®] SmPC, 2021](#)).

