4.3.2. Part 2: Open-Label, Randomized

Part 2 is an efficacy cohort where subjects are randomized to receive Arm A or Arm B as follows:

Arm A:

[figure not shown]
Treatment consists of the combination of plamotamab, tafasitamab, and lenalidomide administered in 28-day cycles, with 2 priming doses of tafasitamab before Cycle 1. Plamotamab and tafasitamab can be administered until disease progression, unacceptable toxicity, or discontinuation for any other reason, whichever comes first. Lenalidomide can be given for up to a total of 12 cycles.

Arm B:

Treatment consists of the combination of tafasitamab and lenalidomide administered in 28-day cycles with 2 priming doses of tafasitamab before Cycle 1. Tafasitamab can be administered until disease progression, unacceptable toxicity, or discontinuation for any other reason, whichever comes first. Lenalidomide can be given for up to a total of 12 cycles.

Part 1 and Part 2 dose and schedule are presented in the schematic below ([Figure 2](#)):

Figure 2: Dosing Schema

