- Subjects who are ineligible for or refuse hematopoietic stem cell transplantation (HSCT). Subjects may be considered ineligible for HSCT for any of the following reasons (Documentation of the reason for a subject's ineligibility must be provided in the subject's source data and electronic case report form [eCRF]):
 - Age
 - Performance status
 - Comorbidities
 - Stem cell mobilization failure
 - Failure of prior transplant
 - Insufficient response to salvage chemotherapy
 - Subject refusal
 - Logistical reasons
 - Other potential reasons not listed above will be considered on a case-by-case basis
- If eligible for CAR-T therapy, subjects must consent to bypassing the approved treatment with demonstrated clinical benefit
- An Eastern Cooperative Oncology Group (ECOG) performance status of 0 to 2 (see [Appendix A](#))
- Completed vaccination for the SARS-CoV-2 virus prior to study entry is recommended

Laboratory Values

- Subjects must meet the following laboratory criteria at screening:
 - $ANC \geq 1.5 \times 10^9/L$ (for subject with bone marrow involvement $ANC \geq 0.5 \times 10^9/L$)
 - Platelet count $\geq 90 \times 10^9/L$ (for subjects with bone marrow involvement platelet count $\geq 50 \times 10^9/L$)
 - Total serum bilirubin $\leq 1.5 \times$ upper limit of normal (ULN), unless secondary to Gilbert's syndrome or documented liver involvement by lymphoma. Subjects with Gilbert's syndrome or documented liver involvement by lymphoma may be included if their total bilirubin is $\leq 5 \times$ ULN

- ALT, AST, and alkaline phosphatase $\leq 3 \times$ ULN, or $< 5 \times$ ULN in cases of documented liver involvement
- Serum creatinine clearance must be ≥ 60 mL/minute calculated using a standard Cockcroft and Gault formula or Modification of Diet in Renal Disease (MDRD; [Levey, 1999](#))
- Willingness to avoid pregnancy or fathering children based on the criteria below.
 - Male subjects with reproductive potential must agree to take appropriate precautions to avoid fathering children (with at least 99% certainty) from screening through 180 days (6 months) after the last dose of study treatment, even if they have undergone a successful vasectomy, and must refrain from donating sperm during this period. Permitted methods that are at least 99% effective in preventing pregnancy (see [Section 6.4](#)) should be communicated to the subjects and their understanding confirmed.
 - Women of childbearing potential subjects:

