 - Must commit either to abstain continuously from heterosexual sexual intercourse or agree to take appropriate precautions to avoid pregnancy (by using 2 different methods of birth control with at least 99% certainty) starting at least 4 weeks before taking the study treatment, while taking the study treatment, during breaks (dose interruptions), and for at least 8 months after stopping the study treatment. Permitted methods that are at least 99% effective in preventing pregnancy (see [Section 6.4](#)) should be communicated to the subjects and their understanding confirmed.
 - Must have a negative serum pregnancy test at screening (within 10 to 14 days of Day –8) and before the first dose of lenalidomide on Day 1 (within 24 hours of initiating treatment with lenalidomide).
 - Agree to ongoing pregnancy testing during the course of the study: weekly during the first month of study drug treatment, then monthly thereafter for women with regular menstrual cycles or every 2 weeks for women with irregular menstrual cycles (even if true abstinence is the chosen method of birth control) up to and including the end-of-treatment (EOT) visit.
 - Must refrain from breastfeeding and donating oocytes during the course of study and for 8 months after the last dose of study treatment.

Note: The subjects should be informed about the option of donation and cryopreservation of germ cells before the study if applicable.

- In the opinion of the Investigator, the subjects must:
 - Be able and willing to receive adequate prophylaxis and/or therapy for thromboembolic events
 - Be able to understand, give written informed consent, and comply with all study-related procedures, medication use, and evaluations

- Not have a history of noncompliance in relation to medical regimens or be considered potentially unreliable and/or uncooperative
- Be able to understand the reason for complying with the special conditions of the protocol and supplemental Summary of Pregnancy Prevention Strategies and give written acknowledgement of this in the informed consent form (ICF)

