6.4. Avoidance of Pregnancy

Lenalidomide, a thalidomide analogue, caused limb abnormalities in a developmental monkey study similar to birth defects caused by thalidomide in humans. If lenalidomide is used during pregnancy, it may cause birth defects or embryo-fetal death. Pregnancy must be

excluded before start of treatment. Prevent pregnancy during treatment by the use of 2 reliable methods of contraception (USPI, Section 5.1). For the most recent information on lenalidomide, see the prescribing information in Revlimid[®] PI, 2021; Revlimid[®] SmPC, 2022.

For the most recent information on tafasitamab, refer to the US PI (Monjuvi[®] PI, 2021) or the European Medicines Agency SmPc (Minjuvi[®] SmPC, 2021).

Subjects receiving tafasitamab and/or lenalidomide should refer to their respective medication guides for more information on avoidance of pregnancy.

Female subjects and male subjects with female partners of childbearing potential must agree to use 2 highly effective methods of birth control during, and after, the last dose of study drug. Women are considered to be of childbearing potential unless there is a documented reason (ie, postmenopausal by history with no menses for 1 year and confirmed by follicle-stimulating hormone [FSH; using local reference ranges], OR history of hysterectomy, OR history of bilateral tubal ligation, OR history of bilateral oophorectomy (CTFG, 2020).

Male subjects will be followed for 6 months, and female subjects 8 months following the last dose of study drug to confirm contraceptive use. If a pregnancy occurs during this timeframe, it will be reported per guidelines in Section 10.4. A woman is considered of childbearing potential, ie fertile, following menarche and until becoming post-menopausal unless permanently sterile. Permanent sterilization methods include hysterectomy, bilateral salpingectomy and bilateral oophorectomy. A postmenopausal state is defined as no menses for 12 months without an alternative medical cause. A high FSH level in the postmenopausal range may be used to confirm a post-menopausal state in women not using hormonal contraception or hormonal replacement therapy. However, in the absence of 12 months of amenorrhea, a single FSH measurement is insufficient. A man is considered fertile after puberty unless permanently sterile by vasectomy or bilateral orchiectomy (CTFG, 2020).

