7. TREATMENT OF SUBJECTS

7.1. Dosing Schedule and Premedications

7.1.1. Plamotamab Dosing Schedule and Premedications

Subjects in Part 1 and those randomized to Arm A in Part 2 will be administered plamotamab IV [REDACTED] In Cycle 1, plamotamab will be administered once every 7 days (\pm 1 day) for 4 doses; beginning with Cycle 2, plamotamab will be administered every 2 weeks.

Subjects in Cohort 1A and Cohort 1B receive plamotamab according to the doses and schedule in [Table 12](#).

Table 12: Cohorts 1A and 1B Plamotamab Dosing Regimen

Cohort	Dose Level	Cycle 1 Day 1 (Priming Dose)	Cycle 1 Day 8	Cycle 1 Day 15	Cycle 1 Day 22	Cycle 2 Day 1	Cycle 2 Days 1, 8, 15, and 22	Cycle 3 and Subsequent Q2W Dosing
1A	-1	0.8 mg	2 mg	20 mg	20 mg	20 mg	20 mg	20 mg
1B	1	0.8 mg	2 mg	20 mg	35 mg	50 mg	50 mg	50 mg

Q2W = every 2 weeks.

The dose and schedule of plamotamab for Part 2 will be determined in Part 1.

Adjustments may be made to the infusion rate to increase the length of infusion time based on the Investigator's judgement of safety. Due to pump accuracy variations, infusions ending within 5 minutes prior to the required [REDACTED] period will not be considered a deviation.

Administer plamotamab at least 2 hours after tafasitamab on days when both products are given. All subjects in Part 1 and randomized to Arm A in Part 2 will be premedicated for plamotamab doses as indicated in [Table 13](#).

Table 13: Premedications for Plamotamab

	Cycle 1	Subsequent Cycles
Dexamethasone (if plamotamab alone is administered)	20 mg IV approximately 1 hour prior	Optional
Diphenhydramine	25 mg PO or IV approximately 30 to 60 minutes prior	Required
Acetaminophen	650 mg PO approximately 30 to 60 minutes prior	Required

IV = intravenous; PO = by mouth.

Subjects who have received 4 consecutive infusions at a stable dose and schedule without CRS or infusion reactions may have their premedications modified at the discretion of the Investigator.

In the event of the discontinuation of plamotamab, in the absence of disease progression, and if the subject is still receiving benefit from the study treatment, subjects may continue with other study treatment(s).

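### Section 10.4.2 allows a decision that ends in continued breastfeeding with plamotamab stopped, which conflicts with the breastfeeding ban in Section 6.1 and the synopsis; a minor safety-text correction

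*Protocol*

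**What the plan says.** The protocol states a breastfeeding rule in three places.

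- **Section 6.1 and the synopsis (inclusion criteria)** carry the same requirement: "Must refrain from breastfeeding and donating oocytes during the course of study and for 8 months after the last dose of study treatment". In both places it is a sub-item under "Women of childbearing potential subjects".
- **Section 10.4.2 (Breastfeeding)** says it is unknown whether plamotamab passes into milk and gives its reason for caution: "Since it is known that antibodies can be secreted in human milk, a risk to the newborns/infants cannot be excluded". It then directs: "A decision should be made whether to discontinue breastfeeding or to discontinue plamotamab", with the value of nursing to the child balanced against the value of the drug to the woman. It names no other drug and gives no period after the last dose.

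Two other parts of the protocol bear on how these fit together. Section 7.1.1 lets a subject who stops plamotamab continue the other study treatment if her disease has not progressed and she still benefits. Section 2.3.2 describes one of those other treatments: "Tafasitamab is a humanized CD19-directed cytolytic monoclonal antibody".

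**The concern.** The two rules give different answers to the same question. Under Section 6.1 a woman of childbearing potential may not breastfeed at any time on study or in the 8 months after her last dose. Under Section 10.4.2 the investigator and subject may weigh benefits and decide that she continues to nurse, at the price of stopping plamotamab.

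What is at stake is the safety of an infant. A site that took 10.4.2 at face value could accept breastfeeding while tafasitamab infusions continue, or within the 8 months after the last dose. For a woman of childbearing potential that breaches 6.1. It could also expose the child to an antibody, which is the hazard that 10.4.2 itself cites. The documents give no data on lenalidomide in milk, so nothing is claimed about it. No endpoint, sample size or analysis is involved.

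**Working it through.** No arithmetic applies; the check is a comparison of texts.

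**Step 1. The rules side by side.**

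| | Section 6.1 and synopsis | Section 10.4.2 |
|---|---|---|
| Form | Mandatory | Decision by weighing benefits |
| Can breastfeeding continue? | No | Yes, if plamotamab is stopped |
| Drugs covered | All study treatment | Plamotamab only |
| Period after last dose | 8 months | Not stated |
| Who is covered | Women of childbearing potential | Not restricted by fertility, but relevant only to women on plamotamab |

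The synopsis repeats 6.1, so this is one rule stated twice against one differing paragraph. It is not a majority of independent statements. The silence of 10.4.2 on a post-dose period is not in itself a contradiction, since 6.1 supplies one. The contradiction lies in the second row.

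**Step 2. Does stopping plamotamab reconcile them?** It does not, for three reasons.

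- The subject remains on study. Section 6.3.2 lists what takes a subject off study: screen failure, completing the 5-year follow-up, withdrawal from study and follow-up, and death. Stopping one drug is not on the list.
- The 8 months in 6.1 run from the last dose of study treatment, not of plamotamab alone.
- Section 7.1.1 allows the other drugs to continue, and Section 7.1.2 gives tafasitamab to every subject. The reasoning in 10.4.2 about antibodies in milk applies to tafasitamab as much as to plamotamab.

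**Step 3. Does another clause settle which rule prevails?** Section 7.5 requires every inclusion criterion to be met, Section 7.4 has the Medical Monitor or a designee confirm eligibility, and Section 12.2 bars deviations except in a medical emergency. These strengthen 6.1, but no clause states that 6.1 overrides 10.4.2. The withdrawal criteria in 6.3.1 deal with pregnancy and do not mention breastfeeding. The exclusion criteria (6.2), pregnancy avoidance (6.4), concomitant medications (7.2) and the lenalidomide section (10.4.3) contain no breastfeeding rule either.

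**Step 4. Who could be affected?** Section 10.4.1 discontinues a subject who becomes pregnant on treatment. The realistic case is therefore a woman nursing a child born before she entered. If she is of childbearing potential, 6.1 already binds her. A woman outside that category is not covered by the 6.1 item. Section 6.4 exempts women with a documented reason, such as "OR history of hysterectomy, OR history of bilateral tubal ligation, OR history of bilateral oophorectomy". A second definition later in 6.4 lists hysterectomy, bilateral salpingectomy and bilateral oophorectomy but not tubal ligation, and the contraception list there includes bilateral tubal occlusion. Hysterectomy and bilateral oophorectomy are thus examples outside the category under both definitions; tubal ligation is not.

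**The case against.** The strongest reply is that the mandatory rule already controls. Section 6.1 is phrased as a must and 10.4.2 as a should. The criterion is verified before entry, and deviations are barred. A site reading the whole protocol would apply the stricter text, and harm would require it to follow 10.4.2 while ignoring a criterion it had confirmed. Much of this stands, and it is why the point is minor. It does not remove the conflict. The criterion is checked at screening, whereas 10.4.2 is the section titled for the subject and the natural place to look during treatment. It should not offer an option that 6.1 forbids.

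A second reply is that 10.4.2 never says that plamotamab alone stops or that the ban is waived. That is correct. A reader might infer that 10.4.2 authorises breastfeeding on tafasitamab, but the text does not say so. The scenario comes from joining 10.4.2 to the general permission in 7.1.1. The supported statement is narrower: 10.4.2 allows breastfeeding to continue, and nothing in it requires the other drugs to stop.

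A reader might also infer that women outside the childbearing-potential category have no rule in Arm B, where "Treatment consists of the combination of tafasitamab and lenalidomide administered in 28-day cycles" and no plamotamab is given. The documents do not support that. Section 2.4.3 has tafasitamab and lenalidomide given according to their labels apart from the tafasitamab run-in. Section 6.4 points to both products' labels and medication guides, and Section 10.4.3 sends other reproductive questions to the lenalidomide prescribing information. Section 6.1 also mentions a separate pregnancy-prevention summary. These sources were not available and may address lactation. Arm B was in any case never reached: Section 4.1.2 required evaluation of at least 40 Part 1 subjects and a revised protocol first.

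Finally, the group outside childbearing potential is very narrow: in practice, a woman nursing an infant after surgical sterilisation and after at least 1 prior line of therapy. Nothing in the documents suggests that such a subject was expected. This stands, and it makes widening the ban a secondary matter.

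**Conclusion.** The conflict is real and sits in the current text. Section 10.4.2 permits an outcome that Section 6.1 and the synopsis forbid, and stopping plamotamab does not cure it because another antibody may continue.

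It is a minor safety-text correction. The affected group is very small, the entry criterion already covers nearly all of it, and nothing statistical changes. The SAP (Section 1) records early termination with 3 subjects enrolled, so the correction matters mainly if the protocol is amended or its text reused.

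The conclusion rests on two readings: that the sentence in 10.4.2 means what it says in allowing breastfeeding to continue, and that no clause in the protocol ranks 6.1 above it. It does not depend on the unseen labels. Whatever they say about tafasitamab or lenalidomide, they would not remove a conflict between two sections of this protocol.

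**What to change.** **Main change.** Replace the decision sentence in Section 10.4.2 with wording such as:

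> In line with Section 6.1, female subjects must not breastfeed at any time during the study, nor in the 8 months that follow their final dose of plamotamab, tafasitamab or lenalidomide, whichever comes last.

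The 8 months are the sponsor's own figure in Section 6.1 and the synopsis. They also match the contraception period in Section 6.4, which runs from the last of the three drugs.

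**Secondary tidy-up.** In Section 6.1 and the synopsis, move the breastfeeding requirement out of the childbearing-potential sub-list so that it covers all female subjects. An infant's exposure through milk does not depend on whether the mother can conceive again. The oocyte-donation part can stay where it is.

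**Cost.** Three short text edits, with no change to visits, data collection or analysis. Section 12.3 requires IRB/IEC approval of every amendment, so the edits are best carried with another revision. The one that Section 4.1.2 planned before Part 2 would have served; with the study terminated, the place for them is any later amendment or protocol that reuses this text.

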10.4.3. Embryo-Fetal Toxicity from Lenalidomide WARNINGS AND PRECAUTIONS Section

Lenalidomide is a thalidomide analogue and is contraindicated for use during pregnancy. Thalidomide is a known human teratogen that causes life-threatening human birth defects or embryo-fetal death (see [Revlimid[®] PI, 2021](#), “Use in Specific Populations” [8.1]). An embryo-fetal development study in monkeys indicates that lenalidomide produced malformations in the offspring of female monkeys who received the drug during pregnancy, similar to birth defects observed in humans following exposure to thalidomide during pregnancy.

Women of Childbearing Potential:

Women of reproductive potential must avoid pregnancy for at least 4 weeks before beginning lenalidomide therapy, during therapy, during dose interruptions and for at least 4 weeks after completing therapy. Females must commit either to abstain continuously from heterosexual sexual intercourse or to use 2 methods of reliable birth control, beginning 4 weeks prior to initiating treatment with lenalidomide, during therapy, during dose interruptions and continuing for 4 weeks following discontinuation of lenalidomide therapy. Two negative pregnancy tests must be obtained prior to initiating therapy. The first test should be performed within 10 days and the second test within 24 hours prior to prescribing lenalidomide therapy. Thereafter, tests should occur weekly during the first month, then monthly thereafter in females with regular menstrual cycles, or every 2 weeks in females with irregular menstrual cycles.

Males:

Lenalidomide is present in the semen of subjects receiving the drug. Therefore, males must always use a latex or synthetic condom during any sexual contact with females of reproductive potential while taking lenalidomide and for up to 4 weeks after discontinuing lenalidomide, even if they have undergone a successful vasectomy. Male subjects taking lenalidomide must not donate sperm.

Blood Donation:

Subjects must not donate blood during treatment with lenalidomide and for 4 weeks following discontinuation of the drug because the blood might be given to a pregnant female subject whose fetus must not be exposed to lenalidomide.

Pregnancy Exposure Registry:

There is a pregnancy exposure registry that monitors pregnancy outcomes in females exposed to lenalidomide during pregnancy as well as female partners of male subjects who are exposed to lenalidomide. This registry is also used to understand the root cause for the pregnancy. Report any suspected fetal exposure to lenalidomide to the Sponsor.

Risk Summary:

Based on the mechanism of action (see [Revlimid[®] PI, 2021](#), “Clinical Pharmacology” [12.1]) and findings from animal studies (see Data)], lenalidomide can cause embryo-fetal harm when administered to a pregnant female and is contraindicated during pregnancy (see [Revlimid[®] PI, 2021](#) for Boxed Warning, “Contraindications” [4.1], and “Use in Specific Populations” [8.0]). Lenalidomide is a thalidomide analogue. Thalidomide is a human teratogen, inducing a high frequency of severe and life-threatening birth defects such as amelia (absence of limbs), phocomelia (short limbs), hypoplasticity of the bones, absence of bones, external ear abnormalities (including anotia, micropinna, small or absent external auditory canals), facial palsy, eye abnormalities (anophthalmos, microphthalmos), and congenital heart defects. Alimentary tract, urinary tract, and genital malformations have also been documented and mortality at or shortly after birth has been reported in about 40% of infants. Lenalidomide caused thalidomide-type limb defects in monkey offspring. Lenalidomide crossed the placenta after administration to pregnant rabbits and pregnant rats [see Data]. If this drug is used during pregnancy, or if the subject becomes pregnant while

taking this drug, the subject should be apprised of the potential risk to a fetus. If pregnancy does occur during treatment, immediately discontinue the drug. Under these conditions, refer subject to an obstetrician/gynecologist experienced in reproductive toxicity for further evaluation and counseling. Report any suspected fetal exposure to lenalidomide to the Sponsor. The estimated background risk of major birth defects and miscarriage for the indicated population is unknown. All pregnancies have a background risk of birth defect, loss, or other adverse outcomes. The estimated background risk in the US general population of major birth defects is 2% to 4% and of miscarriage is 15% to 20% of clinically recognized pregnancies.

Please also refer to lenalidomide prescribing information for pregnancy prevention and other reproductive, issue-related questions ([Revlimid[®] PI, 2021](#)).

